Safety analyses will be based on the safety population. All AEs will be coded using the Medical Dictionary for Regulatory Activities (MedDRA) and preferred term. All AEs with onset date on or after the first dose of double-blind study medication and prior to 7 days after the permanent discontinuation of study medication (onset date – last date of dose <=7) will be summarized using discrete summaries at the subject and event level by system organ class and preferred term for each treatment group. AEs with onset date after Visit 7, will be summarized in the OLE study (810P304) for subjects who decide to enroll in the OLE. Similarly, treatment-emergent AEs will be summarized by severity and relationship separately. Vital signs and all other safety endpoints will be summarized using descriptive statistics by treatment groups. If applicable, categorical laboratory tests will be summarized using number and percent of subjects by treatment groups. Data on infrequent behaviors will be listed.

IA Diary Cross-Validation:

Cross-validation model generated based on the results from the validation of the IA diary in the 810P301 and 810P302 studies may be used to predict and estimate the accuracy of electronic IA diary to measure aggressive behaviors in adolescents.

Pharmacokinetic Analysis:

Bioanalytical Analysis:

Pharmacogenomics (PGx) Analysis:

The DNA will be extracted and tested for any genetic variations associated with CYP2D6 enzyme. The residual DNA will be stored for possible testing of genes involved in the efficacy and possible association with particular adverse events of the drug (e.g., understand the nonresponders to treatment and/or individuals who show unusual safety profile). The DNA analysis will not be used for individual genetic characterization and the subject identity will be kept confidential. The PGx report will be a stand-alone document.

TITLE F	PAGE	
SUPER	NUS PH	IARMACEUTICALS, INC. PROTOCOL APPROVAL PAGE
SUMM	IARY OF	CHANGES4
CLINIC	AL PRO	TOCOL SYNOPSIS
LIST O	F TABLE	S AND FIGURES
	F ABBRI	EVIATIONS
1.	ETHICS	5
	1.1	Institutional Review Boards / Independent Ethics Committees
	1.2	Ethical Conduct of the Study
	1.3	Investigators and Study Personnel
	1.4	Subject Information and Consent/Assent
2.	INTRO	DUCTION
	2.1	Background
	2.2	Impulsive Aggression Comorbid with ADHD
	2.3	Current Treatment Options
	2.4	Sponsor's Phase 2 Studies
	2.5	Sponsor's Phase 3 Studies
	2.6	IA Diary
	2.7	Study Rationale
3.	STUDY	OBJECTIVES
	3.1	Primary Objective

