6.4.6 Laboratory Measurements

With the exception of urine pregnancy test, clinical laboratory tests will be performed by a central laboratory as specified in the reference binder.

Details for collecting, handling, and shipping samples (including shipment addresses) will be detailed in a separate laboratory manual. The Schedule of Visits and Procedures (Table 1) shows the time points at which urine samples will be collected for urinalysis and blood samples will be collected for clinical laboratory tests and plasma concentration levels.

Table 3 presents the clinical laboratory tests to be performed. Metabolic parameters (including insulin, glucose, triglycerides, and cholesterol) and prolactin will be measured. A subject will be excluded if the Screening blood test results indicates > 2 times the upper limit of normal (ULN) of alanine aminotransferase (ALT), aspartate aminotransferase (AST), gamma glutamyl transpeptidase (GGT), and/or serum creatinine. Laboratory tests will not be repeated for these subjects.

All laboratory tests will be reviewed in a timely manner by qualified site personnel to ensure safety. Abnormal lab findings may be confirmed if necessary by one repeated testing at the discretion of the Investigator. Any repeat laboratory testing will be conducted under **fasting condition**. Any laboratory abnormality may qualify as an AE in the Investigator's judgment.

Category	Parameters
Hematology	RBC, WBC, Hgb, HCT, MCH, MCHC, MCV, platelet count, and WBC with differential (neutrophils, lymphocytes, monocytes, eosinophils, basophils, large unstained cells)
Chemistry	Electrolytes: Na ⁺ , K ⁺ , chloride, bicarbonate
	Liver function tests: alkaline phosphatase, AST, ALT, total bilirubin, direct bilirubin ,indirect bilirubin
	Renal function parameters: BUN, creatinine
	Other: glucose, Ca ⁺² , albumin, phosphorus, lactate dehydrogenase, total protein, CK/CPK, globulin, uric acid, triglycerides, insulin, prolactin, cholesterol – total, HDL and LDL Amylase, gammaGT (GGT), Iron, Lipase, Magnesium
Urinalysis	Glucose, protein (total), ketones, bilirubin, urobilinogen, hemoglobin, leucocyte esterase, nitrite
Urine	Cocaine, amphetamines, barbiturates, benzodiazepines, cannabinoids, opioids, phencyclidine, propoxyphene, methadone and alcohol
Urine Pregnancy Test	hCG

Table 3 Clinical Laboratory Tests

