9.5.4 Laboratory Values

Clinical laboratory values will be summarized by visit and by treatment group using descriptive statistics for hematology and chemistry. For quantitative laboratory parameters, both actual values and change from Baseline values will be summarized.

Laboratory test results will be assigned a low, normal, high (LNH) classification according to whether the values were below (L), within (N), or above (H) the laboratory parameters' reference ranges provided by the central laboratory. Within-treatment comparisons will be based on three by three tables (shift tables) that, for a particular laboratory test, compare the LNH classification at baseline to the LNH classification at visit. By subject-listings of all abnormal laboratory values, i.e., those with L or H classification will be provided.

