9.5.6 ECG Results

Tabular summaries of the quantitative ECG parameters and the overall ECG findings (normal, abnormal not clinically significant, or abnormal clinically significant) will be presented. The QT will be corrected using Fridericia's method.

ECG results will be summarized by visit and by treatment group using descriptive statistics (for quantitative ECG parameters) and frequency tables (for qualitative ECG parameters, including the overall ECG finding). For quantitative ECG parameters, both actual values and change from Baseline values will be summarized.

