## **7.2** Clinical Laboratory Tests

The absolute value and change from baseline to EOS for laboratory tests will be summarized using descriptive statistics (n, mean, standard deviation, median, minimum, and maximum) by Treatment groups, laboratory category (Chemistry, Hematology, Immunochemistry, and Urinalysis). The summary will be presented by Treatment group in for Chemistry, Hematology, Immunochemistry and Urinalysis respectively. Subject listings of clinical laboratory data will be presented.

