#### **7.4** ECG

The absolute value and change from baseline to EOS for ECG parameters (heart rate, PR interval (msec), QRS interval (msec), QT interval (msec), and QT corrected for heart rate using Fridericia's (QTcF) correction formula, RR interval (msec)) will be summarized using descriptive statistics for continuous variable by treatment groups as described in Section 5.1. Subject listings of ECGs will be presented.

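### SAP 7.2 applies means and SDs to urinalysis, and SAP 7.2 and 7.4 drop, without explanation, the protocol's laboratory shift tables and overall ECG finding

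*SAP*

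**What the plan says.** **Laboratory tests, SAP 7.2.** Absolute values and changes from baseline to EOS "will be summarized using descriptive statistics (n, mean, standard deviation, median, minimum, and maximum) by Treatment groups, laboratory category (Chemistry, Hematology, Immunochemistry, and Urinalysis"). The next sentence of that section names urinalysis again. Subject listings follow. No other laboratory table is specified.

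**Laboratory tests, protocol.** Table 3 in section 6.4.6 gives the urinalysis panel: "Glucose, protein (total), ketones, bilirubin, urobilinogen, hemoglobin, leucocyte esterase, nitrite". Section 9.5.4 opens: "Clinical laboratory values will be summarized by visit and by treatment group using descriptive statistics for hematology and chemistry". It then classifies each result as low, normal or high against the central laboratory's reference ranges and adds: "Within-treatment comparisons will be based on three by three tables (shift tables"). It also promises: "By subject-listings of all abnormal laboratory values, i.e., those with L or H classification will be provided". The safety paragraph of the synopsis says: "If applicable, categorical laboratory tests will be summarized using number and percent of subjects by treatment groups".

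**ECG.** Protocol 9.5.6 plans summaries of the interval measurements and also says that "the overall ECG findings (normal, abnormal not clinically significant, or abnormal clinically significant) will be presented", as frequency tables by visit and arm. SAP 7.4 lists heart rate and the PR, QRS, QT, QTcF and RR intervals, which "will be summarized using descriptive statistics for continuous variable by treatment groups as described in Section 5.1". Listings follow there too.

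**The concern.** Two things in the SAP sections look wrong.

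First, the SAP prescribes one set of continuous statistics for every laboratory category. Some urinalysis tests, nitrite and leucocyte esterase for example, are likely to be reported as a grade. For a graded result, a mean, an SD or a change from baseline depends on whatever numeric codes the programmer assigns, so the table would not describe the patients.

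Second, the protocol's categorical safety tables do not appear in the SAP. Those tables answer a question that continuous summaries cannot: how many subjects in each arm moved from normal to abnormal. For laboratory tests and ECGs in an adolescent antipsychotic trial, that count by arm is the usual basis for comparing safety. Without it, a reader would have to build the count from listings.

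**Working it through.** There is no figure to reproduce. The check is a comparison of the two documents.

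| Item | Protocol | SAP |
|---|---|---|
| Continuous laboratory summaries | Hematology and chemistry (9.5.4) | Chemistry, hematology, immunochemistry and urinalysis (7.2) |
| Categorical laboratory tests | Number and percent by arm, if applicable (synopsis) | Not mentioned in 7.2 |
| Low/normal/high shift tables | Three by three, baseline against visit, within treatment (9.5.4) | Absent |
| Listing of out-of-range values | By subject (9.5.4) | General laboratory listing only (7.2) |
| ECG intervals and heart rate | Continuous summaries (9.5.6) | Continuous summaries (7.4) |
| Overall ECG finding, three classes | Frequency tables by visit and arm (9.5.6) | Absent from 7.4 |

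**Urinalysis.** Table 3 names eight tests and no result format. If k of the eight are graded, the statistics in SAP 7.2 are unsuitable for k tests and usable for the other 8 − k, with k anywhere from 0 to 8. Two things in the protocol point away from k = 0: 9.5.4 leaves urinalysis out of its continuous summaries, and the synopsis provides for categorical laboratory tests.

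**What subject-level information remains by arm under the SAP.**

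1. Minimum and maximum in SAP 7.2, and those plus quartiles for ECG through SAP 5.1. A maximum shows the most extreme subject in an arm. It does not show how many subjects were out of range.
2. Adverse event tables. Protocol 6.4.6 makes a laboratory abnormality an adverse event at the investigator's judgment. Protocol 6.4.2 includes a laboratory or ECG deterioration that causes symptoms, a change in treatment or discontinuation. These events are counted by arm in SAP 7.1.1.
3. Listings, which give no counts.

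The gap is therefore the abnormal result that nobody reported as an adverse event. It is not counted by arm anywhere.

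**Visits.** Table 1 schedules laboratory tests at Visit 7, the end of maintenance, and at Visit 8, which it labels EOS and which follows the 10-day conversion or taper. SAP 7.2 names change to EOS only, whereas the protocol's shift tables are by visit. A restored table should therefore show Visit 7 as well. Table 1 schedules ECGs at Screening and Visit 7 only.

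**Scope.** SAP 5.1 limits the analysis because the study was halted, but it keeps clinical laboratory evaluations and ECG results in scope. It gives no reason for dropping these tables.

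**The case against.** **The SAP is allowed to differ.** Protocol 8.1 lets the SAP supersede the protocol's statistical methods, and SAP 5.1 announces a reduced analysis after two studies showed no efficacy. This stands: a reader might infer a breach of the protocol, and there is none. But because the SAP controls, a table that it omits will not be produced, and its stated reduction does not cover laboratory or ECG data.

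**SAP 5.1 already has a rule for categorical variables.** It does, as frequency and percentage. Sections 7.2 and 7.4 do not call on it, and 7.2 names continuous statistics for urinalysis outright, so the specific text conflicts with the general rule.

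**The urinalysis format is not documented.** This stands. A reader might infer that all eight tests are categorical and that the whole table is invalid. No section gives the format, the synopsis sentence is conditional, and naming hematology and chemistry in 9.5.4 does not state that urinalysis is excluded. The criticism has to be conditional on graded results.

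**Averages are not all that is left.** This also stands. A reader might infer that the SAP replaced counts with means, or that individual abnormalities are not summarized by arm at all. The protocol already planned means for quantitative laboratory and ECG values. The SAP keeps them, adds medians and extremes (and quartiles for ECG), and counts by arm whatever is reported as an adverse event.

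**The planned sample size does not measure the loss.** A reader might illustrate it with 93 subjects per arm, or argue that this drug's harms show up as a few extreme values. The SAP gives no achieved number after the halt, and neither document describes how laboratory or ECG harms would be distributed.

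**Conclusion.** The point holds in limited form and is minor. The urinalysis instruction in SAP 7.2 is wrong for any graded test: between 0 and 8 of the panel, probably including nitrite and leucocyte esterase, on the assumption that these are reported as grades. Separately, and whatever the urinalysis format, two sets of tables specified in the protocol are missing from the SAP without explanation: the laboratory shift tables and the overall ECG finding. The consequence is that laboratory and ECG abnormalities not reported as adverse events have no count by arm. The low rating reflects the halted study and the purely descriptive analysis. No primary or key secondary result is affected.

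**What to change.** - **SAP 7.2:** limit the continuous summaries to tests reported as quantities. Report graded urinalysis results as n (%) by arm. Confirm each test's result format with the central laboratory first.
- **SAP 7.2:** restore the low/normal/high shift tables of protocol 9.5.4 as n (%) by arm and by visit, including Visit 7.
- **SAP 7.4:** restore the overall ECG finding of protocol 9.5.6 as n (%) by arm and by visit.
- If any of these tables is left out on purpose, say so in the SAP and give the reason.

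The cost is a wording change and a few standard tables from data that the protocol already plans to hold. One check is needed: the three-class ECG reading is named only in the analysis section (9.5.6), while 6.4.9 mentions interval measurements and investigator review. Confirm that the classification was captured before committing to that table.

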# **7.3** Vital Signs

The absolute value and change from baseline to EOS for vital signs (body temperature, heart rate, respiration rate, systolic blood pressure, weight, height, BMI and diastolic blood pressure) will be summarized using descriptive statistics for continuous variables by treatment group as described in Section 5.1. The summary will be presented by treatment groups. Subject listings of Vital signs will be presented.

#### **7.4** ECG

The absolute value and change from baseline to EOS for ECG parameters (heart rate, PR interval (msec), QRS interval (msec), QT interval (msec), and QT corrected for heart rate using Fridericia's (QTcF) correction formula, RR interval (msec)) will be summarized using descriptive statistics for continuous variable by treatment groups as described in Section 5.1. Subject listings of ECGs will be presented.

#### **7.5** C-SSRS

C-SSRS outcomes will be summarized using number and percent of subjects by categories for Actual Attempts, suicidal ideation, suicidal behavior, and suicidality (ideation and behavior combined). The summary will be presented by treatment group. C-SSRS will be presented in Listings.

# **7.6** Extrapyramidal Symptoms

Extrapyramidal Symptoms collected using Simpson-Angus Scale, Barnes Akathisia Scale, and Abnormal Involuntary Movement Scale will be summarized and listed by treatment group.
